5.7 Study Drug

Study drugs refer to drugs that are used (or can be used) in this study to assess the safety and the efficacy of the Investigational Product. Investigators will assess the relationship of adverse events to the use of study drugs.

Study drug will be provided by AbbVie and administered on Day 1, and subjects will not be retreated ([Table 1](#)).

Table 1. Study Drug Information

| Product | Mode of Administration | Formulation | Total Treatment Dose | Manufacturer |
|-----------------------------|-------------------------|---------------------|----------------------|--------------|
| BOTOX Cosmetic (100 U/vial) | Intramuscular Injection | Powder for solution | 64 U | Allergan |

Study drug provided by AbbVie should not be substituted or alternately sourced unless otherwise directed by AbbVie. Upon receipt, study drug should be stored as specified on the package insert and kept in a secure location. Study drug will only be used for the conduct of this study.

Additional information regarding the study drug and administration is available in the Operations Manual ([Appendix E](#)).

5.8 Randomization/Drug Assignment

All subjects who provide informed consent will be assigned a unique subject identification number at the Day 1 visit. For subjects who rescreen, the subject identification number assigned at the initial Day 1 visit should be used.

Randomization is not applicable since this is an open-label study.

5.9 Protocol Deviations

AbbVie does not allow intentional/prospective deviations from the protocol except when necessary to eliminate an immediate hazard to study subjects. The investigator is responsible for complying with all protocol requirements, written instructions, and applicable laws regarding protocol deviations. If a protocol deviation occurs (or is identified, including those that may be due to the COVID-19 pandemic), the investigator is responsible for notifying IEC/IRB, regulatory authorities (as applicable), and AbbVie.

5.10 Data Monitoring Committee

A data monitoring committee is not planned for this study.

6 SAFETY CONSIDERATIONS

6.1 Complaints and Adverse Events

Complaints

A complaint is any written, electronic, or oral communication that alleges deficiencies related to the physical characteristics, identity, quality, purity, potency, durability, reliability, safety, effectiveness, or performance of a product/device. Complaints associated with any component of this investigational product must be reported to AbbVie.

Product Complaint

A product complaint is any complaint related to the biologic or drug component of the product or to the medical device component(s).

For a product this may include, but is not limited to, damaged/broken product or packaging, product appearance whose color/markings do not match the labeling, labeling discrepancies/inadequacies in the labeling/instructions (e.g., printing illegible), missing components/product, device damage or not working properly, or packaging issues.

Product complaints concerning the investigational product and/or device must be reported to AbbVie within 24 hours of the study site's knowledge of the event.

Reporting will be done via electronic data capture (EDC). The date the product complaint details are entered into EDC and the form is saved represents the date reported to AbbVie. A back-up paper form will be provided for reporting complaints related to unassigned product or in the event of an EDC system issue. If a back-up paper form is used, the date the form is emailed to [contact] represents the date reported to AbbVie.

All follow-up information is to be reported to the sponsor (or an authorized representative) and documented in source as required by the sponsor. Product complaints associated with AEs will be reported in the study summary. All other complaints will be monitored on an ongoing basis. Product complaints occurring during the study will be followed up to a satisfactory conclusion.

Medical Complaints/Adverse Events and Serious Adverse Events

An AE is defined as any untoward medical occurrence in a subject or clinical investigation subject administered a pharmaceutical product and which does not necessarily have a causal relationship with this treatment. An AE can therefore be any unfavorable and unintended sign (including an abnormal laboratory finding), symptom, or disease temporally associated with the use of a medicinal (investigational) product, regardless of whether the event is considered causally related to the use of the product.

Such an event can result from use of the drug as stipulated in the protocol or labeling, as well as from "special situations" such as accidental or intentional overdose, medication error, occupational or accidental exposure, off-label use, drug abuse, drug misuse, or drug withdrawal, all which must be reported whether associated with an AE or not. Any worsening of a pre-existing condition or illness is considered an AE. Worsening in severity of a reported AE should be reported as a new AE. Laboratory abnormalities and changes in vital signs are considered to be AEs only if they result in discontinuation from the study, necessitate therapeutic medical intervention, and/or if the investigator considers them to be AEs.

The investigators will monitor each subject for clinical and laboratory evidence of AEs on a routine basis throughout the study. All AEs will be followed to a satisfactory conclusion.

An elective surgery/procedure scheduled to occur during a study will not be considered an AE if the surgery/procedure is being performed for a pre-existing condition and/or the surgery/procedure has been pre-planned prior to study entry. However, if the pre-existing condition deteriorates unexpectedly during the study (e.g., surgery performed earlier than planned), then the deterioration of the condition for which the elective surgery/procedure is being done will be considered an AE.

If an AE, whether associated with study drug or not, meets any of the following criteria, it is to be reported to AbbVie clinical pharmacovigilance as a SAE within 24 hours of the site being made aware of the SAE (refer to Section 4.2 of the Operations Manual for reporting details and contact information):

| | |
|---|--|
| Death of Subject | An event that results in the death of a subject. |
| Life-Threatening | An event that, in the opinion of the investigator, would have resulted in immediate fatality if medical intervention had not been taken. This does not include an event that would have been fatal if it had occurred in a more severe form. |
| Hospitalization or Prolongation of Hospitalization | An event that results in an admission to the hospital for any length of time or prolongs the subject's hospital stay. This does not include an emergency room visit or admission to an outpatient facility. |
| Congenital Anomaly | An anomaly detected at or after birth, or any anomaly that results in fetal loss. |
| Persistent or Significant Disability/Incapacity | An event that results in a condition that substantially interferes with the activities of daily living of a study subject. Disability is not intended to include experiences of relatively minor medical significance such as headache, nausea, vomiting, diarrhea, influenza, and accidental trauma (e.g., sprained ankle). |

**Important Medical Event
Requiring Medical or Surgical
Intervention to Prevent
Serious Outcome**

An important medical event that may not be immediately life-threatening or result in death or hospitalization but based on medical judgment may jeopardize the subject and may require medical or surgical intervention to prevent any of the outcomes listed above (e.g., death of subject, life threatening, hospitalization, prolongation of hospitalization, congenital anomaly, or persistent or significant disability/incapacity). Additionally, any elective or spontaneous abortion or stillbirth is considered an important medical event along with any suspected transmission of an infectious agent via a medicinal product if no other serious criterion is applicable. Examples of such events include allergic bronchospasm requiring intensive treatment in an emergency room or at home, blood dyscrasias or convulsions that do not result in inpatient hospitalization, or the development of drug dependency or drug abuse.

All adverse events from the time of study drug administration will be collected for at least 30 days or until the last follow-up visit, whichever is longer, whether solicited or spontaneously reported by the subject. After 30 days following the last dose of study drug or last follow-up visit, whichever is longer, only spontaneously reported SAEs will be collected (nonserious AEs will not be collected). In addition, study procedure-related serious and nonserious adverse events will be collected from the time the subject signs the study-specific informed consent.

The following definitions will be used for Serious Adverse Reactions (SAR) and Suspected Unexpected Serious Adverse Reaction (SUSAR):

| | |
|--------------|--|
| SAR | Defined as all noxious and unintended responses to an Investigational medicinal product (IMP) related to any dose administered that result in an SAE as defined above. |
| SUSAR | Refers to individual SAE case reports from clinical trials where a causal relationship between the SAE and the IMP was suspected by either the sponsor or the investigator, is unexpected (not listed in the applicable Reference Safety Information) and meets one of the above serious criteria. |

AbbVie will be responsible for SUSAR reporting for the IMP in accordance with global and local requirements.

Adverse events will be monitored throughout the study to identify any of special interest that may indicate a trend or risk to subjects.

Adverse Event Severity and Relationship to Study Drug

The investigators will rate the severity of each AE as mild, moderate, or severe.

The investigator will use the following definitions to rate the severity of each AE:

| | |
|-----------------|---|
| Mild | The adverse event is transient and easily tolerated by the subject. |
| Moderate | The adverse event causes the subject discomfort and interrupts the subject's usual activities. |
| Severe | The adverse event causes considerable interference with the subject's usual activities and may be incapacitating or life threatening. |

The investigator will use the following definitions to assess the relationship of the AE to the use of study drug:

| | |
|----------------------------------|--|
| Reasonable Possibility | After consideration of factors including timing of the event, biologic plausibility, clinical judgment, and potential alternative causes, there is sufficient evidence (information) to suggest a causal relationship. |
| No Reasonable Possibility | After consideration of factors including timing of the event, biologic plausibility, clinical judgment, and potential alternative causes, there is insufficient evidence (information) to suggest a causal relationship. |

Pregnancy

While not an AE, pregnancy in a study subject must be reported to AbbVie within 24 hours after the site becomes aware of the pregnancy. Subjects who become pregnant during the study will be encouraged to remain in the study for follow-up through study exit but will receive no further treatment with the study drug. If a pregnancy occurs in a study subject, information regarding the pregnancy and the outcome will be collected. Partner pregnancy information will not be collected.

The pregnancy outcome of an elective or spontaneous abortion, stillbirth or congenital anomaly is considered a SAE and must be reported to AbbVie within 24 hours after the site becomes aware of the event.

Possible Distant Spread of Toxin

Possible distant spread of toxin (PDSOT) is defined as a possible pharmacologic effect of botulinum toxin at sites noncontiguous and distant from the site of injection. Utilizing a standardized methodology to assess for PDSOT, MedDRA preferred terms (PTs) that may be associated with botulinum toxin effects have been prospectively identified (see the statistical analysis plan [SAP] for a complete list of these PTs). Adverse events reporting any of these terms will be medically reviewed on a regular basis throughout the study and will be summarized in the clinical study report.

7 STATISTICAL METHODS & DETERMINATION OF SAMPLE SIZE

7.1 Statistical and Analytical Plans

The statistical methods provided in this protocol will be focused on primary and secondary efficacy endpoints. Complete and specific details of the statistical analysis will be described in the SAP.

7.2 Definition for Analysis Populations

The mITT population includes all enrolled subjects who receive the total dose of 64 U of BOTOX Cosmetic, as described in this study protocol.

The Safety Analysis Set consists of all subjects who receive at least 1 injection of study drug.

7.3 Handling Potential Intercurrent Events for the Primary and Secondary Efficacy Endpoints

Observed data will be used without imputation, so subjects who have an intercurrent event resulting in not having a Day 30 assessment for any reason will not be included. Intercurrent events include:

- Subjects who are enrolled but do not receive the total dose of 64 U of BOTOX Cosmetic, as described in this study protocol
- Subjects who are enrolled but prematurely discontinue the study before the Day 30 assessment
- Subjects who die before the Day 30 assessment
- Subjects who are lost to follow-up and are missing Day 30 data for the endpoint
- Subjects who continue in the study beyond Day 30, but are missing the Day 30 assessment for any reason

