3 OBJECTIVES AND ENDPOINTS

3.1 Objectives, Hypotheses, and Estimands

Objective

The objective of this study is to evaluate subject satisfaction and natural outcomes following the administration of 64 U of BOTOX Cosmetic in subjects with upper facial lines (GL, LCL, and FHL).

Clinical Hypothesis

Single treatment of upper facial lines with BOTOX Cosmetic at 64 U can lead to subject satisfaction and natural outcomes.

Estimands

The estimand corresponding to the primary endpoint is as follows:

- The proportion of subjects receiving treatment of BOTOX Cosmetic 64U who achieve the responder status of *Mostly satisfied* or *Very satisfied* on the Facial Line Satisfaction Questionnaire (FLSQ) Item 4 at the Day 30 assessment in the modified intention-to-treat (mITT) population. Subjects who have any intercurrent event resulting in not having a Day 30 assessment will not be included.

The estimand corresponding to the secondary endpoint is as follows:

- The mean change from baseline in subject assessment based on Rasch-transformed score of FACE-Q Psychological Function at the Day 30 assessment for subjects who receive BOTOX Cosmetic 64 U in the MITT population. Subjects who have any intercurrent event resulting in not having a Day 30 assessment will not be included.

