4.2 Discussion of Study Design

Choice of Control Group

This is an open-label study. There is no separate control group.

Appropriateness of Measurements

The primary efficacy measure used in this study (FLSQ) is a validated measure. Allergan has also developed and validated upper facial line severity scales (AGLSS, LCLSS, and FHLSS) in accordance with the United States Food and Drug Administration requirement. All efficacy-related measurements in this study are standard for assessing facial aesthetics correction (for GL, LCL, and FHL). All clinical procedures in this study are standard and generally accepted.

Suitability of Subject Population

The study population will include male and female adults with moderate to severe GL, LCL, and FHL at maximum contraction as assessed by investigators using the AGLSS, LCLSS, and FHLSS, respectively. To avoid confounding the study results, washout from prior facial aesthetic treatments is required as described in the eligibility criteria.

Selection of Doses in the Study

BOTOX Cosmetic is currently approved for aesthetic treatment of GL, LCL and FHL. The total dose, dilution, injection pattern, and route of administration will follow the approved label, and each eligible subject will receive a fixed dose of 64 U of BOTOX Cosmetic on Day 1 (20 U to the glabellar complex, 24 U to the lateral canthal areas, and 20 U to the frontalis muscles).

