5.3 Prohibited Medications and Procedures

The decision to administer a prohibited medication/treatment during the study period is done with the safety of the subject as the primary consideration. When possible, the sponsor is to be notified before the prohibited medication/treatment is administered.

In addition to the medications listed in the eligibility criteria, no other facial cosmetic procedures or treatments are to be performed throughout the duration of the study. Prohibited treatments and procedures include, but are not limited to:

All other investigational drugs are prohibited.

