5.4 Prior and Concomitant Procedures

Any medication or vaccine (including over-the-counter or prescription medicines, vitamins, and/or herbal supplements) that the subject is receiving at the time of enrollment or receives during the study must be recorded from 30 days prior to the study drug administration through the study exit. See below for details on special handling for the COVID-19 vaccine.

The use of any medication during the study (including prescription or over-the-counter medication, vitamins, and/or herbal supplements) is to be recorded on the subject's electronic case report form (eCRF) at each visit along with the reason the medication is taken, dates of use, and dosing regimen. Concomitant medications and concurrent procedures will also be collected at each visit.

Study site personnel should notify the sponsor immediately if a subject uses a concomitant medication or has a concurrent procedure that is prohibited per protocol (see Section 5.3). Subjects who use prohibited concomitant medications or have a prohibited concurrent procedure may be discontinued at the discretion of the investigator or sponsor. Concomitant medications and concurrent procedures will be tabulated and listed.

Non-live vaccines may be used during the study, if not contraindicated or medically inappropriate. When possible, study drug should be given at least \pm 7 days from vaccine administration.

Co-administration of aminoglycosides or agents that could interfere with neuromuscular transmission (e.g., curare-like agents) or muscle relaxants are to be used with caution as the effects of the toxin, theoretically, could be potentiated.

Systemic and topical hormones and their derivatives (e.g., sex steroids - androgens, estrogens, progesterone) should be maintained throughout the study period to avoid changes in skin, including but not limited to:

- Oral birth control
- IUDs/implants/injections
- Oral supplements including testosterone & estrogens and their derivatives, dehydroepiandrosterone (DHEA), etc.
- Topicals (anywhere on the body) including testosterone & estrogens and their derivatives, DHEA, etc.
- Androgel, Axiron, Testim, Fortesta, Vogelxo
- Emedelle (methyl estradiolpropanoate), Rejuvenate, All Natural Bioidentical Estradiol, Emerita Phytoestrogen

Subjects should maintain their skin care regimen throughout the study period.

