5.6 Follow-Up After Subject Discontinuation of Study Drug or from Study

To minimize missing data for efficacy and safety assessments, subjects should continue to be followed for all regularly scheduled visits, unless subjects have decided to discontinue the study participation entirely (withdrawal of informed consent). Subjects should be advised on the continued scientific importance of their data.

If a subject prematurely discontinues study participation (withdrawal of informed consent), the procedures outlined for the Early Exit visit should be completed as soon as possible, preferably within 2 weeks. In addition, if subject is willing, a 30-day follow-up phone call after the last dose of study drug may be completed to ensure all treatment-emergent adverse events (TEAEs)/serious adverse events (SAEs) have been resolved.

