7.8 Sample Size Determination

No formal sample size calculation was performed.

For a conservative expected proportion of 75% for the primary endpoint (proportion of subjects reporting *Mostly satisfied* or *Very satisfied* on the FLSQ Follow-up Item 4 at Day 30), a sample size of 100 subjects in the study is required for an adjusted logit-based 95% binomial confidence interval to have a width of 16.8% (interval is 75% – 9.1% to 75% + 7.7% with recommended correction of – 1/2).⁹

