8.0 Handling of Potential Intercurrent Events for the Primary and Key Secondary Endpoints

Observed data will be used without imputation, so subjects who have an intercurrent event resulting in not having FLSQ Item 4 at Day 30 for any reason will not be included in the primary efficacy endpoint. Intercurrent events include:

- Subjects who are enrolled but do not receive any study drug;
- Subjects who are enrolled and treated but prematurely discontinue the study before assessment of the primary endpoint;
- Subjects who die before assessment of primary endpoint;
- Subjects who are lost to follow-up and are missing assessment of primary endpoint;
- Subjects who are missing assessment of primary endpoint for any other reason (including COVID) not mentioned above
 - The same approach will be used for the secondary analysis.

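### Should other botulinum toxin or a prohibited facial procedure before Day 30 be named as an intercurrent event?

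*Protocol*

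**What the plan says.** The estimands in Protocol 3.1 deal with intercurrent events only through their effect on data availability: "Subjects who have any intercurrent event resulting in not having a Day 30 assessment will not be included". Protocol 7.3 repeats this: "Observed data will be used without imputation, so subjects who have an intercurrent event resulting in not having a Day 30 assessment" are left out. Its list covers incomplete dosing, discontinuation before Day 30, death, loss to follow-up and a missed Day 30 assessment. SAP 8.0 has a similar list, and its rule for the primary endpoint is that "subjects who have an intercurrent event resulting in not having FLSQ Item 4 at Day 30 for any reason will not be included"; the secondary one is treated likewise. SAP 9.2 rules out imputation for efficacy. SAP 9.3.3 plans no sensitivity or supplementary analysis.

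The conduct sections treat other facial treatments as relevant. Protocol 4.2 says: "To avoid confounding the study results, washout from prior facial aesthetic treatments is required as described in the eligibility criteria". Protocol 5.3 says that "no other facial cosmetic procedures or treatments are to be performed throughout the duration of the study". Under Protocol 5.4, "Subjects who use prohibited concomitant medications or have a prohibited concurrent procedure may be discontinued at the discretion of the investigator or sponsor". Protocol 5.6 asks that "subjects should continue to be followed for all regularly scheduled visits, unless subjects have decided to discontinue the study participation entirely".

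**The concern.** The stated aim is satisfaction and natural outcomes after one 64 U treatment. A subject who has another toxin or a facial procedure in the first month may answer FLSQ Item 4 or FACE-Q on the combined result. The protocol sees this risk when it requires washout and bans further procedures, yet the estimands do not mention it. The only rule attached to the intercurrent-event lists concerns a missing value, whereas this event leaves a value in place and may change its meaning.

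Discontinuation after prohibited treatment is also discretionary. In an open-label study, one affected subject could stay and be counted while another is discontinued before Day 30 and leaves the denominator. With no supplementary analysis planned, a reader might be unable to tell whether such events moved the responder rate or the FACE-Q change. One subject weighs more in the SAP 9.6 subgroups, four of which should hold about 20 people each.

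**Working it through.** **1. Does the plan fix the handling?** Three rules apply together:

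- mITT membership depends only on receiving the full 64 U (Protocol 7.2, SAP 4.0).
- Observed data are used without imputation (Protocol 7.3 and 7.4, SAP 9.2 and 9.3.2).
- A subject with no Day 30 value is not included (Protocol 3.1 and 7.3, SAP 8.0).

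Applied to a fully dosed subject who has such treatment before Day 30:

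| Situation | Result under the plan |
|---|---|
| Stays and answers at Day 30 | Counted as observed |
| Discontinued before Day 30, no Day 30 answer | Not included; a listed intercurrent event in both documents |
| Stays but misses the Day 30 assessment | Not included; also listed |

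Every case has one answer, so two programmers working independently would produce the same rate.

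**2. Can the effect be seen afterwards?** Protocol 5.4 records medications with dates of use, collects procedures at each visit, and has both tabulated and listed. SAP 7.4 lists subjects with deviations, including use of excluded medications. The SAP version history states that listings of the primary and secondary endpoints are provided. Cross-referencing these listings gives the Day 30 answers of affected subjects.

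**3. The plan's own precision.** Inputs from Protocol 7.8: n = 100, expected proportion 75%, so x = 75. With the -1/2 correction in the centre of the logit interval:

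- centre = ln(74.5/24.5) = 1.112
- standard error = sqrt(1/75 + 1/25) = 0.231
- limits = 1.112 ± 1.96 × 0.231, back-transformed to 65.9% and 82.7%

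This reproduces the stated -9.1/+7.7 points and the width of 16.8. The Clopper-Pearson interval that SAP 9.1 specifies is 65.3% to 83.1%, a width of 17.8 points.

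**4. How far could the rate move?** The documents give no event rate, so k, the number affected, is an assumption. Starting from 75/100 observed:

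| k | Plan (kept as observed) | Left out, all responders | Left out, all non-responders | All responders, rescored as non-responders |
|---|---|---|---|---|
| 1 | 75.0% | 74/99 = 74.7% | 75/99 = 75.8% | 74/100 = 74.0% |
| 3 | 75.0% | 72/97 = 74.2% | 75/97 = 77.3% | 72/100 = 72.0% |
| 5 | 75.0% | 70/95 = 73.7% | 75/95 = 78.9% | 70/100 = 70.0% |
| 10 | 75.0% | 65/90 = 72.2% | 75/90 = 83.3% | 65/100 = 65.0% |

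If 3% to 5% were affected and their satisfaction were 90% instead of 75%, the overall rate would rise by 0.03 × 15 = 0.45 to 0.05 × 15 = 0.75 points. Neither the 3% to 5% nor the 90% comes from the documents.

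**5. Subgroups.** At 15/20 = 75%, leaving out one affected responder gives 14/19 = 73.7%, and rescoring that subject gives 14/20 = 70%. The exact interval for 15/20 is 50.9% to 91.3%, a width of 40.4 points.

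No similar figure can be given for FACE-Q, because the documents state no standard deviation.

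**The case for a change.** The strongest case for a change is the discretion in Protocol 5.4. The same event can keep a subject in the denominator or remove them, depending on a decision made case by case without blinding. Stating the handling in advance and adding one supplementary table would cost little, since the data are already collected.

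Part of this stands. The event is not named, the conduct sections do regard it as a source of confounding, and no planned table links it to the endpoints. Protocol 5.6 favours continued follow-up but does not override the discretion.

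The rest is weaker than it looks:

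- **Discontinuation.** Leaving before Day 30 is already a listed intercurrent event, whatever the reason. Day 30 is also the first scheduled clinic visit after treatment, so a site would often learn of the event when the endpoint is recorded. The activity schedule is not visible, so earlier contacts cannot be excluded.
- **Stating the strategy.** Writing treatment policy into the text leaves the discretion, the population and the main result as they are.
- **A supplementary table.** Leaving out affected subjects selects on a post-treatment event. Counting them all as non-responders, including those discontinued, would assign outcomes to people with no answer, against SAP 9.2 unless an exception were written. With few events, either version would sit close to the main result.

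**Conclusion.** No change is needed. This is a gap in labelling that the general observed-data rule fills sensibly. Naming the strategy would change the reported rate by zero points. For an assumed one to five affected subjects of 100, leaving them out would shift a 75% rate by between -1.3 and +3.9 points. The extremes require all five to be responders or all five non-responders. Rescoring five responders as non-responders would cost 5.0 points. All of this lies within an exact interval 17.8 points wide, in a single-arm study with no hypothesis test. Ten affected subjects could matter more, but nothing in the documents points to that number.

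The conclusion assumes that such events are uncommon in the first month and that the planned listings are produced. The itemised prohibited list in Protocol 5.3 and the text of SAP 9.5 are not visible, so neither the likely frequency nor the direction of any effect can be derived. If the documents are amended for other reasons, a sentence in Protocol 3.1 and 7.3 and in SAP 8.0 saying that the observed Day 30 answer is used regardless of such treatment would be a harmless clarification.
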